6.4. Worst-case

A worst-case analysis visit will be created for parameters for which abnormalities and/or toxicity grades (e.g., labs, vital signs, ECGs) are defined to summarize values considered as the worst-case. For abnormalities worst-case is derived per parameter and in case both the lowest and the highest values are considered abnormal, a participant can have two worst-case analysis visits for a same parameter. For toxicity grades the worst-case is the value associated with the highest toxicity grade and is derived per parameter and toxicity direction (hypo / hyper).

All non-missing post-baseline values, including unscheduled assessments will be considered when deriving the worst-case analysis visit.

Copyright © 2009, 2010, 2012, 2016, 2018, 2019, 2021, 2024 IQVIA. All rights reserved. The contents of this document are confidential and proprietary to IQVIA Holdings Inc. and its subsidiaries. Unauthorized use, disclosure or reproduction is strictly prohibited.

6.5. Treatment-emergent Abnormality/Toxicity

A treatment-emergent abnormality/toxicity (for laboratory assessments, vital signs, or ECGs) is defined as any postbaseline abnormality/toxicity that was not present at baseline (e.g. hemoglobin normal at baseline and grade 1 postbaseline; glucose low at baseline and high postbaseline; QTcF [450; 480] ms at baseline and >500 ms postbaseline).

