2. INTRODUCTION

Participants will be enrolled from both active and placebo arms of qualifying efgartigimod studies in adult patients with pSS. The protocol will be amended to add additional studies at a later date.

In qualifying study ARGX-113-2106, the efficacy and safety of efgartigimod in adult patients with pSS was evaluated using a randomized, double-blinded, placebo-controlled study design. Participants were randomized to receive efgartigimod IV 10 mg/kg or matching placebo in a 2:1 ratio. The IMP (efgartigimod or matching placebo) was administered during the treatment period in approximately 1-hour IV infusion QW by site or a home nurse. The final dose was administered at week 23. At week 24, eligible participants from ARGX-113-2106 may roll over into the present single-arm OLE study: ARGX-113-2211.

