3. OBJECTIVES, ENDPOINTS, AND ESTIMANDS

Table 2: Study ARGX-113-2211 Objectives and Endpoints

Objectives	Endpoints
Primary	

 To evaluate the long-term safety of efgartigimod in patients with pSS 	
 Incidence and severity of AEs and AESIs, incidence SAEs, changes in laboratory test results, vital signs, and ECG results
Secondary	

 To evaluate effect and assess long-term data on durability of CRESS response 	
 Proportion of CRESS responders on ≥ 3 of 5 items at weeks 24 and 48 (refer to Section 8.2.1). The 5 items are: 
 Systemic disease activity: clinESSDAI Patient-reported symptoms: ESSPRI Tear gland function: Schirmer’s test and OSS Salivary gland function: UWSF rate and SGUS Serology: serum IgG and/or RF

 To evaluate the effect of efgartigimod on clinical efficacy parameters 	
 Proportion of participants with minimal clinically important improvement from baseline in ESSDAI: improvement of ≥ 3 points in ESSDAI score at weeks 24 and 48 Proportion of participants with low disease activity: ESSDAI score of < 5 at weeks 24 and 48 Proportion of participants with minimal clinically important improvement from baseline in clinESSDAI: improvement of ≥ 3 points in clinESSDAI score at weeks 24 and 48 Proportion of participants with low disease activity: clinESSDAI score of < 5 at weeks 24 and 48 Proportion of participants with minimal clinically important improvement from baseline in ESSPRI: decrease of ≥ 1 point or $\geq 15\%$ at weeks 24 and 48 Change from baseline in ESSDAI score at weeks 24 and 48 Change from baseline in clinESSDAI score at weeks 24 and 48 Change from baseline in ESSPRI score at weeks 24 and 48

 To evaluate the effect of efgartigimod on STAR 	
 Proportion of STAR responders (score of ≥ 5) at weeks 24 and 48 when compared to baseline

Objectives	Endpoints

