9.3. Statistical Analyses

9.3.1. General Considerations

- Data collected will be listed with derived variables. Descriptive statistical methods will be used to analyze safety and efficacy data
- The results of this study will not be used inferentially
- No formal sample size calculation is presented
- Summaries will include the number of observations (n), mean, SE, 90% CI, median, minimum, and maximum for continuous measures
- Summaries will include sample size, frequencies, and percentages for categorical variables
- The baseline value will be the last assessment before the first administration of the study drug in OLE
- All study visits will be recalculated based on actual dates. The rules for calculating the analysis visits will be documented in the SAP
- Rules for imputing partial dates or missing dates will be provided in the SAP
- Exposure to IMP will be summarized
- TEAEs, AESIs, SAEs, and other safety parameters will be summarized
- AEs will be classified using the latest version of the MedDRA classification system
- AEs, AESIs, and SAEs will be listed corresponding to MedDRA SOC and PT

- Multiple occurrences of a single PT in a participant will be counted only once at the maximum severity/grade
- AEs with missing severity or relationship to IMP will be classified as severe and treatment-related, respectively. All AEs will be summarized by relatedness to IMP
- Any AEs leading to death or discontinuation of IMP will also be summarized
- Population PK/PD analysis may be performed based on the PK and PD data and reported separately
- Laboratory parameters, physical examinations, vital sign measurements, ECG data and PK, PD, immunogenicity, and biomarker results will be summarized descriptively

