6.2. Baseline

Unless otherwise specified, baseline is defined as the last available non-missing measurement from the parent study 2106. Refer to [appendix 1](#) baseline for details. These baseline observations could be either from week 24 or prior visits of ARGX-113-2106. All baseline assessments will be performed before first administration of efgartigimod in ARGX-113-2211, if applicable. The baseline of ECG parameters should come from the same date. If an individual

confidential and proprietary to IQVIA Holdings Inc. and its subsidiaries. Unauthorized use, disclosure or reproduction is strictly prohibited.

ECG parameter is not reported on the latest date prior to 1st IMP infusion within the extension study, leave blank. Assessments do not need to be repeated if they are performed as part of the last visit of the qualifying study. Assessments performed on the same day as the first IMP administration but without time information collected or with time information exactly equal to the time of first IMP administration and which are planned predose will be considered as predose. For parameters related to questionnaires, the baseline is the last value before or at the day of first administration of the IMP, independent of the time of administration. In case the participant never received IMP, the date/time of enrolled will be used instead of first IMP administration date/time. Adverse Events (AEs) and medications commencing on the reference start date will be considered post-baseline unless otherwise indicated based on available start date/time combination or collected electronic case report form (eCRF) information that identifies the individual event/medication as starting prior to first IMP administration.

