For the reporting of descriptive statistics for PK data, the mean and SD will be presented to one digit more precision than the source data except values ≥ 1000 which will be presented without the decimals and rounded to the nearest integer. The minimum, median, and maximum will be presented to the same precision as the source data. Coefficient of variation will always be reported to 1 decimal place. Individual serum concentrations will be reported as received by the bioanalytical laboratory.

Descriptive statistics for immunogenicity titer values will include the number of observed values, arithmetic mean, SE, 90% CI, median, Q1, Q3, minimum, maximum, the geometric mean, and geometric CV%.

For event-type safety data, the number and percentage of participants with an event will be shown. The denominator will be all participants in the analysis set.

For frequency tabulations and cross-tabulations, the denominator will be the number of participants. For tables where results are shown by analysis visit, the denominator will be the number of participants and analysis visit.

Missing values will not be included in the denominator count when computing percentages. For cross-tabulation of post-baseline results versus baseline results, a “missing” category will be shown for baseline results, if applicable. Percentages will be presented with 1 decimal place.

Summaries will be provided both for the overall study population as well as grouped according to treatment received in the parent study AGRX-113-2106 (efgartigimod or placebo). [Appendix 1](#) shows conventions for presentation of data in outputs.

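### Treatment-emergent laboratory and ECG counts, and the safety shift and change tables, use an OLE-entry baseline that is on-drug for former-efgartigimod participants and drug-free for former-placebo participants

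*SAP*

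**What the plan says.** Protocol Section 3 includes "changes in laboratory test results, vital signs, and ECG results" in the primary safety endpoint. Under SAP 6.5, a treatment-emergent abnormality or toxicity in these data "is defined as any postbaseline abnormality/toxicity that was not present at baseline".

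SAP 6.2 sets the reference: "Unless otherwise specified, baseline is defined as the last available non-missing measurement from the parent study 2106". It adds: "These baseline observations could be either from week 24 or prior visits of ARGX-113-2106". It also points to a baseline entry in SAP Appendix 1 for details. Protocol 9.3.1 uses the same concept: "The baseline value will be the last assessment before the first administration of the study drug in OLE".

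Protocol Section 2 describes the parent study as weekly dosing of efgartigimod or placebo, randomised 2:1. On timing it says: "The final dose was administered at week 23. At week 24, eligible participants from ARGX-113-2106 may roll over". Inclusion criterion 4 (Protocol 5.1) requires treatment to continue without a break.

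SAP 7.2 presents summaries overall and "grouped according to treatment received in the parent study". The outputs that depend on baseline are:

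- **Laboratory (SAP 17.1.2):** change-from-baseline summaries, shift tables and treatment-emergent counts.
- **ECG (SAP 17.1.3):** shift tables, treatment-emergent counts and QTc-change categories.
- **Vital signs (SAP 17.1.4):** shift tables only. No treatment-emergent count is named.

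**The concern.** One rule is applied to two groups whose reference values mean different things. For a former-placebo participant, baseline is a state without efgartigimod. For a former-efgartigimod participant, it is a state reached after about 24 weeks on the drug. An abnormality that the drug produced during the parent study and that is still there at rollover becomes part of the reference.

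Two readings are then at risk. Side by side, the group with the longer exposure can show fewer treatment-emergent laboratory or ECG abnormalities only because its earlier ones sit in the baseline. Pooled, the overall column mixes change since starting efgartigimod with change since OLE entry, so it can understate any effect that appears early and lasts. The study's stated purpose is long-term safety, so persistent effects are of direct interest.

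**Working it through.** The documents give no rate or count for this point, so there is no planned figure to reproduce. The check has two parts: timing, which comes from the documents, and an illustration, which rests on assumptions.

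**Timing.** The last parent dose is at week 23 and rollover is at week 24 (Protocol Section 2). The gap is (24 − 23) × 7 = 7 days. SAP 17.1.1 treats 60 days after a dose as still treatment-emergent for adverse events, so by the SAP's own window this baseline is on-drug. If an earlier parent visit supplies the value, it is still on-drug unless it precedes the first parent dose.

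**Exposure.** A former-efgartigimod participant has up to 24 + 48 = 72 weeks on drug. Of these, 24/72 = 33% precede the baseline.

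**Illustration 1: early onset.** Let q be the proportion with a drug-caused abnormality arising in the first 24 weeks of exposure. Let s be the share of these still in the same category at parent week 24. Neither is in the documents; the assumed ranges are q = 10–30% and s = 50–100%. Background is set to zero, with no later onset and no worsening.

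- Former placebo: treatment-emergent rate = q
- Former efgartigimod: rate = q(1 − s)
- Pooled at 2:1: rate = [2q(1 − s) + q]/3 = q(1 − 2s/3)

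Take 30 participants (the approximate maximum in Protocol 9.5) split 20 and 10, which assumes that rollover keeps the 2:1 ratio. With q = 20%:

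| s | Former placebo | Former efgartigimod | Pooled | Against pre-drug baseline |
|---|---|---|---|---|
| 100% | 2/10 = 20% | 0/20 = 0% | 2/30 = 6.7% | 20% |
| 50% | 2/10 = 20% | 2/20 = 10% | 4/30 = 13.3% | 20% |

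The pooled count captures 1 − 2s/3 of the drug-caused abnormalities, whatever q is. That is 67% at s = 50% and 33% at s = 100%. With a 15/15 split the range is 75% to 50%; with 25/5 it is 58% to 17%.

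Now add later onset of 10% in the OLE among those not yet affected (q = 20%, s = 100%). Former placebo shows 0.20 + 0.80 × 0.10 = 28%, and former efgartigimod shows 0.80 × 0.10 = 8%.

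**Illustration 2: steady onset.** Assume a constant hazard, full persistence and 30% affected by 48 weeks.

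- By 24 weeks: 1 − 0.7^(24/48) = 16.3%
- By 72 weeks: 1 − 0.7^(72/48) = 41.4%
- Counted in the OLE, former efgartigimod: 41.4 − 16.3 = 25.1%
- Counted in the OLE, former placebo: 30%

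The crude gap is about 5 points. Among those normal at OLE entry the risk is the same in both groups: 25.1/(100 − 16.3) = 30%. The crude gap appears because participants already abnormal at entry stay in the denominator, which SAP 17.1.2 sets as the participants in the safety set per analysis visit.

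**Mean changes.** If a laboratory shift d is fully reached by OLE entry and then holds, the change from baseline is d in former placebo and about 0 in former efgartigimod. The 2:1 pooled mean is (d + 2 × 0)/3 = d/3.

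**The case against.** The strongest reply is that an OLE-entry baseline answers a legitimate question: what is new in the extension. The protocol chooses it openly and the SAP follows. The first 24 weeks belong to a randomised, placebo-controlled study that can judge drug effects against concurrent controls. The OLE tests no hypothesis. This stands, and it is why the OLE-entry set should stay. It does not make the two parent-treatment columns comparable, nor does it make the pooled column a measure of change since starting efgartigimod.

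A second reply is that little is hidden. Actual values are summarised. Shift tables show who was abnormal at entry, split by parent treatment. Participants with any postbaseline laboratory abnormality or toxicity of grade 1 or more are listed, whatever their baseline. This also stands in part. These displays show that an abnormality existed at entry, but not whether it preceded efgartigimod or arose on it, and they leave the treatment-emergent counts and changes as they are.

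A third reply concerns scope. A reader might infer that drug effects carried over from the parent study can never count, or that the whole primary endpoint is biased. The documents do not support either. SAP 6.5 itself gives a QTcF worsening from an already raised baseline category as an example that counts. New abnormalities count in both groups. AEs, AESIs and SAEs are classified by onset date (SAP 17.1.1), not by this rule.

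Finally, simply replacing the baseline would bring its own imbalance: up to 72 weeks of exposure against 48. In Illustration 2 that gives 41% against 30%. That objection stands too, so the remedy is an addition and not a replacement.

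**Conclusion.** The point holds in a limited form. For laboratory and ECG treatment-emergent counts, QTc-change categories, laboratory change-from-baseline summaries, and the laboratory, ECG and vital-sign shift tables, the reference is on-drug in one group and drug-free in the other. Abnormalities already present in the same category at OLE entry and not worsening drop out of the former-efgartigimod counts. The columns by parent treatment are not comparable on these outputs, and the pooled column can understate persistent drug effects.

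The direction needs only that some drug-caused abnormalities persist to OLE entry. The size cannot be determined. A reader might take the 20% against 0% contrast as an expected result, but it needs all onset within 24 weeks, full persistence and no later onset or worsening. Under steady onset the crude gap is about 5 points. All these figures assume their rates and persistence, and the pooled ones also assume a parent-treatment split.

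Two limits remain. SAP Appendix 1 was not in the text reviewed, so an exception there cannot be excluded. The study is descriptive, so no error rate or power is affected. This is an inexpensive improvement to how the safety data can be read, not a flaw that invalidates the plan.

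**What to change.** 1. Keep the OLE-entry baseline as the protocol sets it. Label its treatment-emergent counts and changes as new since OLE entry, in particular in the pooled column.
2. In SAP 6.2, 6.5 and 17.1.2 to 17.1.4, add a supplementary set of tables for values observed in the OLE. Judge them against the last value before the participant's first-ever efgartigimod dose: the pre-dose baseline of ARGX-113-2106 for former-efgartigimod participants, and OLE entry for former-placebo participants. Restrict the set to parameters that were collected in 2106.
3. Present this set by parent treatment, showing weeks since first efgartigimod dose. State that exposure differs (up to 72 against 48 weeks) and that the former-efgartigimod group contains only people who completed the parent treatment period on the drug.
4. If SAP Appendix 1 already has a separate safety baseline, cross-refer to it in SAP 6.5.

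The cost is SAP wording and one extra set of tables. No new visits or samples are needed. The SAP already draws height, ongoing medications and ongoing AEs from 2106, and its planned split by parent treatment already needs the parent allocation. The reported abnormality rates may turn out less favourable.

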6.6. Statistical Tests

The default significant level will be (10%); confidence intervals (CIs) will be 90% and all tests will be two-sided, unless otherwise specified in the description of the analyses.

6.7. Values below or Above the Quantification Limit

ADA against efgartigimod: titer of positive ADA samples reported as “negative titer” (refer to [Section 16](#)) will be imputed by 1. Listings will always present “negative titer”.

Safety and PD values expressed as below (or above) the quantification limit will be imputed by the value of the quantification limit itself. For participants with a baseline PD value below/above the quantification limit, the PD parameter will be excluded from the statistical analyses involving change and percent change from baseline. Listings will always show the non-imputed values.

Pharmacokinetic concentrations below the lower quantification limit will be reported in the listings as BLQ. For descriptive statistical analysis, all BLQ values will be set to zero. Listings will always present BLQ.

6.8. Common Calculations

For quantitative measurements, change from baseline will be calculated as:

- Test Value at Visit X – Baseline Value

A percent change from baseline can be calculated as;

Percent change from baseline at Visit X = (actual value at Visit X -baseline value) *100/baseline value.

Copyright © 2009, 2010, 2012, 2016, 2018, 2019, 2021, 2024 IQVIA. All rights reserved. The contents of this document are confidential and proprietary to IQVIA Holdings Inc. and its subsidiaries. Unauthorized use, disclosure or reproduction is strictly prohibited.

6.9. Software Version

All analyses will be conducted using SAS version 9.4 or higher.

7. STATISTICAL CONSIDERATIONS

7.1. Missing Data

For imputation of missing values related to efficacy and safety, see appropriate section of the applicable endpoints. Missing efgartigimod concentrations will not be imputed.

7.2. Output Presentations

For continuous variables, full descriptive statistics will only be presented if there are at least 2 non-missing observations. Alternatively, only the number of non-missing data points and mean are shown.

Descriptive statistics for safety and efficacy will include the number of non-missing data points, the arithmetic mean, the standard deviation (SD), the median, minimum, Q1, Q3, maximum, and for efficacy the standard error (SE) and 90% CI may be provided in addition (refer to output templates for details).

Mean, Q1, Q3 and median will be presented with one more decimal place than the measured values. SE and SD will be presented with two more decimal places than the measured values. Minimum and maximum will be presented with the same number of decimal places as the measured values.

Descriptive statistics for PD parameters will include the number of non-missing data points, the arithmetic mean, the SD, the SE, the 90% CI, the median, minimum, Q1, Q3, and maximum. Descriptive statistics of total IgG levels will be presented in $\mu\text{g/mL}$.

Serum PK concentrations will be summarized using descriptive statistics for $n > 2$ by study day and nominal time point using N (sample size), n (available data), arithmetic mean, SD, geometric mean, mean coefficient of variation (CV), CV%, the geometric CV%, minimum, median and maximum.

Concentrations that are BLQ will be treated as zero for the computation of descriptive statistics. If at least one BLQ value is reported at a specific time point, the geometric mean and geometric CV% for that time point will not be calculated. In addition, if one or more than half of the values per time point are BLQ, the arithmetic mean will be reported as BLQ and SD, CV%, GM, [geometric SD], and geometric CV% will not be calculated and shall be reported as not determined (ND); minimum, median, and maximum shall be reported as BLQ if applicable. If $n \leq 2$, only N, n, minimum, and maximum will be reported.

Copyright © 2009, 2010, 2012, 2016, 2018, 2019, 2021, 2024 IQVIA. All rights reserved. The contents of this document are confidential and proprietary to IQVIA Holdings Inc. and its subsidiaries. Unauthorized use, disclosure or reproduction is strictly prohibited.

For the reporting of descriptive statistics for PK data, the mean and SD will be presented to one digit more precision than the source data except values ≥ 1000 which will be presented without the decimals and rounded to the nearest integer. The minimum, median, and maximum will be presented to the same precision as the source data. Coefficient of variation will always be reported to 1 decimal place. Individual serum concentrations will be reported as received by the bioanalytical laboratory.

Descriptive statistics for immunogenicity titer values will include the number of observed values, arithmetic mean, SE, 90% CI, median, Q1, Q3, minimum, maximum, the geometric mean, and geometric CV%.

For event-type safety data, the number and percentage of participants with an event will be shown. The denominator will be all participants in the analysis set.

For frequency tabulations and cross-tabulations, the denominator will be the number of participants. For tables where results are shown by analysis visit, the denominator will be the number of participants and analysis visit.

Missing values will not be included in the denominator count when computing percentages. For cross-tabulation of post-baseline results versus baseline results, a “missing” category will be shown for baseline results, if applicable. Percentages will be presented with 1 decimal place.

Summaries will be provided both for the overall study population as well as grouped according to treatment received in the parent study AGRX-113-2106 (efgartigimod or placebo). [Appendix 1](#) shows conventions for presentation of data in outputs.

